EEG Cap for Identification of Non-Convulsive Status Epilepticus

NCT# 03138876

February 22, 2017

RESEARCH PROTOCOL OUTLINE

Title: EEG Cap Placement for Expedited Identification of Non-Convulsive Status Epilepticus

Principal Investigator: [name] D.O.

Co-Investigators: [name] M.D., [name] M.D., [name] D.O., [name] M.D., [name] M.D., [name] D.O., [name]

Abstract

Altered mental status (AMS) is one of the most common reasons for inpatient neurology consultation. Non-convulsive status epilepticus (NCSE) is frequently a differential diagnosis of the patient with AMS. NCSE becomes more refractory to treatment after one hour of seizure activity, making rapid identification and treatment of NCSE of great clinical importance. Currently, an EEG technician must be called in from home during non-workday hours in order to obtain a stat EEG. We propose the time required for diagnosis of NCSE in our institution can be significantly decreased with rapid placement of an EEG cap by the onsite neurology residents.

A. Specific Aims

1. Utilize EEG cap for rapid assessment of seizure activity in 20 patients with suspected NCSE
2. Rapid EEG review by on-call resident & attending physicians
3. Employ existing standard of care for NCSE evaluation with standard electrodes as soon as technician can apply them (cap to not delay standard of care)
4. Evaluate endpoints for cap vs. standard electrodes of time from consultation to:
 - a. completed EEG
 - b. Diagnosis or exclusion of NCSE

B. Background and Significance

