At the completion of neurology evaluation, if NCSE is in the differential diagnosis according to institution best practice, then consented participants will undergo placement of a large size, 20-channel EEG cap from Electro-Cap International with a Natus E-2-2520-26 electrode board adapter with initiation of recording. The placement of the EEG cap will be restricted to residents formally trained in its placement by an EEG tech. The EEG-cap is already owned by the Mayo Clinic Neurology department, and therefore we will not require further funds to obtain equipment for this study. This study will only be performed during times when EEG techs are not available onsite for rapid placement of standard 21-channel EEG electrodes, such as during night-call shifts. We will not bill for the EEG cap placement, only the subsequent standard EEG protocol which will be followed after the EEG-cap placement.

Prior to placement of EEG cap, evaluating staff member will request stat standard-electrode EEG. We will record time from neurology consultation request to placement of EEG cap as well as time from consultation request to obtaining a standard EEG. We will also record time to confirmation or exclusion of NCSE. Initial diagnosis or exclusion of NCSE will be performed by on call resident, if they received prior training regarding EEG cap placement, and attending. Secondary quality assessment will be performed by two independent EEG interpreters blinded to clinical history. Secondary assessment will be qualified as acceptable or unacceptable interpretation based on whether greater or less than 50% of the recording is judged interpretable. Secondary assessment will also include interpretation of NCSE by a third independent reader if there is disagreement between first two. The number of patients excluded from the study will also be recorded, including the reason for exclusion.

Specific data points for statistical analysis include:

- Time of consultation
- Time of standard-electrode EEG order
- Time that 10 minutes of EEG have been completed (for both cap & standard-electrodes)
- Time that 20 minutes of EEG have been completed (for both cap & standard-electrodes)
- Time of diagnosis or exclusion of NCSE

Primary outcome measure: time from stat EEG order to diagnosis or exclusion of NCSE

Secondary outcome measures include:

- Overall quality of cap recordings as operationalized by:
 - Aforementioned >50% interpretability

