 - Concordance between cap & standard-electrode diagnostic assessments
- comparison of diagnostic assessments/concordance between 10 and 20 minute captures

Statistical methodology: chi-square and Student T-test will be employed to compare categorical variables.

Data storage and PHI: Initial data collection will be to a password-protected Excel spreadsheet that is only accessible by the study authors. No PHI will be collected, but a unique identifying number will be used to initially distinguish between patients. Data will then be aggregated for statistical analysis. The final paper will only include patient data in aggregate form.

D. Preliminary Studies/Progress Report

EEG is the only definitive way to diagnose NCSE. Although useful, standard surface EEG can be a cumbersome, complex and time-consuming process, all of which can limit its applicability in emergent time-sensitive clinical situations and rural areas without available technology, financial resources or neurophysiologic expertise. EEG headsets, caps or “dry EEG” have been developed and have become commercially available over the past few decades and have been used in multiple brain computer interface (BCI) studies, evoked potentials and biofeedback (Halford, et al, Slater et al). This novel technology does not require measurement of relative electrode differences by EEG technologists or pose increased risk for skin abrasions. Disadvantages EEG caps do exist which may affect its clinical suitability, including movement artifact, sweat artifact and increased weight of the system (Halford, et al).

Some studies have investigated the time differences and validity of EEG headsets versus standard EEG recordings in various clinical scenarios. For instance, a study demonstrated that application of an EEG caps in comparison to a standard EEG was performed over 15 minutes faster, with 87% of the EEG being interpreted as technically adequate. In addition, patients preferred the EEG caps over the standard EEG (Halford, et al). The EEG headset recordings were also felt to be adequate in identifying status epilepticus and were significantly faster to set up (Slater et al). “Light” EEG has also been shown to be comparable to standard EEG in detecting findings suggestive of hepatic encephalopathy, but with higher proportion of light EEG samples being discarded due to artifact (Schiff et al).

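### The one statistical sentence ties both named tests to categorical variables, leaving the primary time outcome without an assigned test and the cap-versus-standard pairing unspecified

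*Combined protocol and SAP*

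**What the plan says.** Section C (Study Design, Methods, & Statistics) has the only statement of method: "Statistical methodology: chi-square and Student T-test will be employed to compare categorical variables". The same section defines the main endpoint: "Primary outcome measure: time from stat EEG order to diagnosis or exclusion of NCSE". That is a duration.

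The comparison is within patient. Section A, item 4, reads "Evaluate endpoints for cap vs. standard electrodes of time from consultation to", and its second limb is "b. Diagnosis or exclusion of NCSE". Section C describes "the subsequent standard EEG protocol which will be followed after the EEG-cap placement", and Section G, item 1d, confirms that the routine EEG is done as well as the cap. Section D also sets the time to interpretation of the cap against that of standard EEG.

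In the data-point list, the completion times carry a both-methods label, for example "Time that 20 minutes of EEG have been completed (for both cap & standard-electrodes". The diagnosis item does not; it reads only "Time of diagnosis or exclusion of NCSE".

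The secondary outcomes in Section C include diagnostic concordance between cap and standard electrodes, and between the 10- and 20-minute captures. No paired or agreement method is named anywhere.

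**The concern.** Read literally, the sentence leaves the primary outcome without a test and gives the t-test a task it cannot do. The natural repair is a t-test for times and chi-square for diagnoses. That still leaves the analyst to decide, possibly with data in hand, whether the time comparison is paired. If the bare test names are taken in their ordinary two-sample sense, within-patient correlation is ignored and the estimate of minutes saved is less precise than the data allow.

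Concordance is paired binary data. An ordinary chi-square compares two positive rates or tests association; neither is agreement. Section B treats the reliability of the cap as the open question, so this matters clinically as well as formally.

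The unlabelled diagnosis time bears on the same comparison. If only one such time per patient were kept, the within-patient difference in time to diagnosis could not be calculated.

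**Working it through.** **Inputs.** From the documents: 20 patients (Sections A and C), with both recordings planned in each. They give no SD, effect size, correlation, alpha or power, so there is no planned figure to reproduce. Assumed: normal times, 20 complete pairs, two-sided 5%, correlation ρ of 0, 0.3, 0.5 or 0.7. One SD means the root mean square of the cap and standard SDs, so s₁² + s₂² = 2.

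**Variance of the paired difference.** V = s₁² + s₂² − 2ρs₁s₂.
- Equal SDs: V = 2 − 2ρ.
- 3:1 SD ratio: s₁² = 0.2, s₂² = 1.8, s₁s₂ = 0.6, so V = 2 − 1.2ρ.

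The 3:1 case is included because a cap placed by onsite residents and a standard EEG that waits for a technician called from home need not have equally variable times.

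**Interval width.** Unpaired half-width is t(38)·√(2/20); paired is t(19)·√(V/20). The ratio is (2.0244/2.0930)·√(2/V) = 0.967·√(2/V).

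**Power at 0.65 SD.** Paired: non-central t, 19 df, non-centrality 0.65·√(20/V). Unpaired power and type I error: simulation, 100,000 or more replicates per cell.

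| | ρ = 0 | 0.3 | 0.5 | 0.7 |
|---|---|---|---|---|
| Width ratio, equal SDs | 0.97 | 1.16 | 1.37 | 1.77 |
| Width ratio, 3:1 | 0.97 | 1.07 | 1.16 | 1.27 |
| Paired power, equal SDs | 49.7% | 64.5% | 78.7% | 94.5% |
| Paired power, 3:1 | 49.7% | 57.7% | 64.5% | 72.6% |
| Unpaired power, either case | about 52% | 52% | 52–53% | 53–54% |
| Unpaired type I error, equal SDs | 5.0% | 2.1% | 0.8% | 0.1% |
| Unpaired type I error, 3:1 | 5.5% | 3.6% | 2.4% | 1.4% |

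At 1.2 SD with equal SDs and ρ = 0.3 / 0.5 / 0.7, unpaired power is 97.9 / 99.1 / 99.8% and paired 99.0 / 99.9 / 100%. At 3:1 the loss is also about 1 point.

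**Concordance (hypothetical tables, n = 20, uncorrected chi-square).**
- *Chi-square on the two positive rates.* Suppose each method flags 4 patients, with 4, 2 or 0 in common. Kappa is 1.00, 0.375 or −0.25, yet the rates are equal, so p = 1.00 every time.
- *Chi-square on the cross-tabulation.* Suppose the cap flags the same 4 patients as standard EEG plus 4 others: both positive 4, cap only 4, standard only 0, both negative 12. Chi-square = 20·(4·12 − 4·0)²/(8·12·4·16) = 7.50, p = 0.006. Observed agreement is 16/20 = 0.80; chance agreement is (8·4 + 12·16)/400 = 0.56; kappa = (0.80 − 0.56)/(1 − 0.56) = 0.55. The test is clearly significant although half the cap positives are unconfirmed.

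**Clock start.** Section A counts from consultation and Section C from the order. For a common start C, (T_standard − C) − (T_cap − C) = T_standard − T_cap, so the raw paired difference is the same either way.

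**The case against.** The strongest reply is that the plan is terse, not wrong. A paired t-test is a Student t-test and McNemar's test is a chi-square test, so the sentence could cover paired versions; its wording is probably a slip. This stands in part. A reader might infer that the protocol has chosen unpaired tests. It has not: it leaves pairing unstated.

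A reader might also infer a risk of false claims that the cap is faster. The calculation shows the reverse: with positive correlation the unpaired test is conservative. If the time saving is large, the test choice hardly affects power, and no figure in the documents says whether 0.65 or 1.2 SD is realistic. The loss in interval width remains whatever the effect size.

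The protocol does not say that chi-square will be applied to concordance, and the tables above are hypothetical. But it names no other method that could serve.

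Section C stores a patient number for initial identification and then aggregates the data. One might infer that pairs will be unlinked; the text does not say so, only that nothing commits to keeping the link. Likewise, the missing label does not show that a second diagnosis time will go uncollected.

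Incomplete pairs are partly covered: recruitment is confined to times without onsite technicians, and "The number of patients excluded from the study will also be recorded, including the reason for exclusion". What has no rule is a patient with only one reading, which can arise if the technician arrives first (Section G, item 1d) or the study is stopped because the patient recovers interaction (Section F).

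**Conclusion.** The point holds as a specification gap that should be fixed. The sentence cannot be applied as written to the primary outcome, and no reading of it states a paired analysis or an agreement measure. The size depends wholly on assumed inputs. For positive correlations of 0.3 to 0.7, an unpaired interval would be 16 to 77% wider than the paired one with equal SDs, and 7 to 27% wider at 3:1. At zero correlation there is no gain; the paired interval is slightly wider. The power gain at 0.65 SD ranges from about 5 to 41 points over those positive correlations and is about 1 point at 1.2 SD. The documents support neither a claim of inflated type I error nor a claim that an unpaired test was chosen. The differing clock start is a wording point and does not alter the raw paired comparison.

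**What to change.** Replace the methods sentence with text such as:

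> Time to diagnosis or exclusion of NCSE will be recorded for cap and for standard EEG and compared within patient by a paired t-test (primary), with the mean paired difference in minutes and its 95% CI. The Wilcoxon signed-rank test is a sensitivity analysis. Pairs stay linked by study number through analysis; incomplete pairs are counted and listed by reason. Concordance between cap and standard, and between 10- and 20-minute captures, is reported as the 2x2 table and percent agreement with exact 95% CI, plus kappa with 95% CI where defined. Exact McNemar is used only for a directional difference.

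Give the diagnosis-time data point the same both-methods label as the completion times, and state one clock start by reconciling Section A with Section C.

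The proviso on kappa is needed because it is undefined if neither method finds a positive. With accurate reading at an assumed prevalence of 5, 10 or 20%, that chance is 0.95²⁰ = 36%, 0.90²⁰ = 12% or 0.80²⁰ = 1%.

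The cost is a few sentences, one extra timestamp per patient if it is not already captured, and about 2 power points at zero correlation (49.7% against about 52% at 0.65 SD). If times are strongly skewed, the paired t-test gives up some power: in a log-normal simulation (log-SD 0.8, shift 0.65 log-SD, correlation 0.3 to 0.7) the signed-rank test gained about 8 to 10 points, which is why it is kept as the sensitivity analysis.

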Data in identifying epileptiform activity or NCSE utilizing EEG caps is lacking. Disposable forehead electrodes have also been shown to identified status epilepticus, although studies have included a limited number of patients with NCSE and the results have been variable (Myllymaa et al) (Muraja-Murro, et al). In one study, only two out of four patients with status epilepticus were identified with forehead electrodes due to EEG abnormalities being restricted to the posterior regions of the brain (Muraja-Murro, et al).

Due to the small sample sizes, limited number of patients with NCSE and variable electrode placements in prior studies, it remains unclear the applicability of EEG caps in the identification of NCSE, which our study seeks to investigate further. In addition, we plan to readdress the quality and interpretability, as well as the time taken from ordering to interpretation of the EEG cap compared to standard EEG.

E. Gender/Minority/Pediatric Inclusion for Research

Gender and ethnicity will not be used as exclusion criteria when selecting patients. The study will include both men and women. Pediatric patients under the age of 18 will be excluded from our study to permit use of adult size EEG cap for all participants.

F. Human Participants

Inclusion:

1. Patients with suspected NCSE in the Mayo Clinic Florida hospital, emergency room or intensive care unit.
2. Age: Patients of 18 years or older will be included in this study

3. Education: All education levels will be included

Exclusion:

1. Patients younger than 18 years of age.
2. Patients with open head trauma.
3. Patients with anatomy that would preclude EEG cap placement.
4. Patients excluded for anatomical or age-related reasons will be tracked to determine applicability of the EEG cap to the patient population at Mayo Clinic.
5. Pregnant females
6. Large head size not amenable to cap placement
7. Scalp infection
8. Inability to obtain informed consent

Informed Consent:

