Given the nature of the project aimed at expeditiously identifying NCSE the following details will be verbally provided to health care proxies prior to placement of the EEG cap:

- The study involves assessing patient brain waves with an experimental EEG cap to attempt to diagnose and treat seizures that do not produce convulsive movements, but can alter mental status.

- The cap could identify seizures before the normal method of analyzing brain waves will be performed, which could potentially allow for earlier treatment.
- There is minimal risk, with main risk being that cap may be inaccurate and might be misinterpreted. The risk of misdiagnoses, leading to inappropriate diagnosis and treatment is likely small, but exact data is not available.
- The normal method of analyzing brain waves will be used either way as fast as possible
- Do not feel obligated to consent if you prefer for our typical protocol to be followed. The patient's overall care, outside of the context of this study, will not change based on your decision.
- If you would like some time to think about this decision, I will attempt to return at a time of your choosing.

G. Risks and benefits:

This study is considered minimal risk given the only deviation from standard of care involves application of EEG cap prior to standard of electrodes. To the extent that cap electrodes might be misinterpreted due to theoretically poorer quality risks include:

- Misinterpretation of EEG so as to miss seizure activity, which would not affect time to treatment, given we will still be following and giving priority to our standard protocol.
- Misinterpretation of EEG so as to diagnose non-seizure activity as epileptiform, which is unlikely as attendings will avoid diagnosing NCSE if there is any uncertainty in the EEG.

1. Procedures protecting against or minimizing potential risks:
 - a. Patients will be evaluated by neurology residents or faculty members
 - b. EEG cap will be applied by neurology staff and cleaned between each use
 - c. Electronic data will be stored in a password-protected Excel spreadsheet that contains no PHI
 - d. Regular EEG protocol will be followed in addition to EEG cap placement. Standard electrode placement will be given priority in the event EEG technician is available before EEG cap is placed. There will be no deviation from the current standard of care.
2. Future benefits and importance to the participants and others:

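### Cap-fit exclusions have no fit criterion, named assessor or cut-off time, so a failed placement can drop out of the quality and time results

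*Combined protocol and SAP*

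**What the plan says.** Section F (Human Participants) lists as exclusion 3 "Patients with anatomy that would preclude EEG cap placement" and as exclusion 6 "Large head size not amenable to cap placement". No head measurement or fit test is attached to either. The section does not say who decides, or when.

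Section C gives the order of events. Neurology evaluation is completed, and if NCSE remains in the differential, "consented participants will undergo placement of a large size, 20-channel EEG cap". Only this one cap size is named. On staff, section C says "The placement of the EEG cap will be restricted to residents formally trained in its placement by an EEG tech", and section G says "Patients will be evaluated by neurology residents or faculty members".

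The first secondary outcome in section C begins "Overall quality of cap recordings as operationalized by", and its first component is whether more than half of the recording can be interpreted. The primary outcome is the time from the stat EEG order to NCSE being diagnosed or ruled out.

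The plan does keep account of exclusions. Section C says "The number of patients excluded from the study will also be recorded, including the reason for exclusion", and item 4 of the exclusion list says that anatomical and age-related exclusions are tracked to judge how widely the cap can be used.

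**The concern.** The study asks whether a cap placed by on-site residents gives a faster and usable EEG. Failure to get the cap onto a head is one answer to that question. Here the same event also fits the wording of an eligibility criterion, and the plan sets no moment at which eligibility closes. A patient whose cap was tried and did not fit can be recorded, in keeping with the text, as someone who should not have been in the study.

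At stake are the share of acceptable recordings and the estimated time saved. Both would then describe only the patients in whom the cap went on. With 20 planned patients, one or two such cases are enough to move the quality figure visibly.

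**Working it through.** **1. What the text allows.** The only design figure is the planned 20 patients (sections A and C). It has no derivation, and no alpha, power or effect size is given, so there is no calculation to reproduce. The check is of the text, followed by an illustration.

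- *Eligibility:* exclusions 3 and 6 have no criterion, assessor or closing point.
- *Sequence:* evaluation, then consent, then placement. No separate fit check is described.
- *Quality:* the two independent readers rate recordings. An attempt without a recording gives them nothing to rate.
- *Time:* the listed data points cover consultation, the standard-EEG order, 10 and 20 minutes completed on each system, and the diagnosis time. There is no entry for a failed attempt and no rule for the time such a patient contributes.
- *Analysis set:* none is defined, and the plan does not say whether excluded patients are replaced to reach 20.

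**2. Illustration for quality.** All counts are assumed. Take 20 recordings with 17 acceptable; this is the whole number nearest to 0.87 × 20 = 17.4, where 87% is the technical adequacy that section D reports for a different headset. Let k further attempts fail and be labelled exclusions. The reported share is 17/20 whatever k is; the share per attempt is 17/(20 + k). Intervals are exact (Clopper-Pearson) 95%.

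| k | Share per attempt | 95% interval |
|---|---|---|
| 0 | 17/20 = 85.0% | 62.1 to 96.8 |
| 1 | 17/21 = 81.0% | 58.1 to 94.6 |
| 2 | 17/22 = 77.3% | 54.6 to 92.2 |
| 3 | 17/23 = 73.9% | 51.6 to 89.8 |
| 4 | 17/24 = 70.8% | 48.9 to 87.4 |
| 5 | 17/25 = 68.0% | 46.5 to 85.1 |

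Each restored failure lowers the share by about 3 to 4 points. If instead the 20 already include the failures and nobody is replaced, then with k = 2 and 16 of 18 recordings acceptable, the report reads 16/18 = 88.9% against 16/20 = 80.0% per attempt.

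**3. Illustration for time.** Assume that a failed attempt saves nothing, so that the patient's cap time equals the standard-EEG time. The mean saving over all attempts is then the mean over successes multiplied by 20/(20 + k). It shrinks by 1 − 20/21 = 4.8% at k = 1, 1 − 20/22 = 9.1% at k = 2, 1 − 20/23 = 13.0% at k = 3 and 1 − 20/25 = 20.0% at k = 5.

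**4. Would it arise at all?** The documents give no failure rate. With independent attempts and an assumed rate p, the chance of at least one failure in 20 is 1 − (1 − p)^20. This is 64% at p = 5%, 88% at 10% and 99% at 20%.

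**The case against.** The strongest reply is that the plan already accounts for exclusions. A fit failure labelled an exclusion would be logged with its reason, and a reader could add it back. This stands in part. It makes a wholly hidden failure unlikely, but nothing requires the log to separate a patient never attempted from one in whom the attempt failed, and nothing returns the second kind to the outcomes.

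A reader might also infer several stronger things that the documents do not support:

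- *That the resident placing the cap judges fit.* Section C restricts placement, not eligibility, to trained residents, and section G has patients evaluated by residents or faculty. Nobody is named as judge of fit.
- *That misfit will often emerge only at the attempt.* Exclusion 3 is worded prospectively, and evaluation precedes capping. The text permits late discovery but does not say how common it is.
- *That every device failure can be excluded.* The two criteria cover anatomy and large heads. Poor contact or artefact meets neither, although an attempt with no recording for such a reason still falls outside a denominator of recordings.

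Two further objections hold. Quality of recordings and applicability of the cap are separate questions, so the recordings-only figure keeps a place. A rule that scored every unfinished placement as a failure would also be unfair to the cap. The Informed Consent text stops the study if the patient becomes able to interact, and section G gives standard electrodes priority if the technician is available before the cap is on. Neither event reflects on the device.

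**Conclusion.** The concern holds as a gap in the eligibility and analysis rules. Cap-fit exclusions can be applied after an attempt, and nothing keeps a failed attempt in the quality or time results. The missing head measurement alone would be a matter of detail; it matters here because the exclusion overlaps with the outcome.

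For quality, the direction follows from arithmetic: dropping failed attempts cannot lower the acceptable share, and it raises that share whenever at least one recording is acceptable. For time, it rests on the assumption that a failed attempt saves nothing and on the cap saving time when it works. It would go too far to say that the results will always favour the cap, because the plan may meet no such failure or may settle fit beforehand.

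The size is unknown. The fall from 85% to 77% with two restored failures uses assumed counts, and at this sample size the 95% interval around 17/20 (62.1 to 96.8) contains every per-attempt share in the table. The case for change is that the bias is avoidable at little cost, not that it is shown to be large.

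**What to change.** In section F, replace the open wording of exclusions 3 and 6 with an objective fit criterion, such as a measured head circumference against a stated limit. The study team must supply the limit, since the documents give no size range for the cap. Name who applies the criterion, require it to be decided and logged before any attempt, and allow no cap-fit exclusion once placement has started.

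In section C, add:

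- The denominator for the interpretability outcome is placement attempts. An attempt that gives no recording for a device or fit reason counts as unacceptable.
- In the time comparison, such a patient's cap time is the time of the standard-EEG diagnosis.
- Attempts ended because the patient became able to interact, or because the technician arrived first, are reported separately with reasons and are not scored as cap failures.
- Pre-attempt exclusions and failed attempts are reported as separate counts. The share of acceptable recordings among recordings obtained is kept as a supplementary result.

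The cost is one extra log field, a brief fit check before placement, a few sentences of text and possibly a lower reported success rate. No additional patients are needed.
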